6.1. Proposed Chronology of Procedures

For the study period described below, when multiple procedures are scheduled at the same time point(s) relative to dosing, the following chronology of events should be adhered to, *where possible*.

- *12-lead ECG*: obtain prior to vital signs assessment, blood samples, and prior to dosing (refer to [Section 7.1.6](#)).
- *Vital Signs (BP and pulse rate)*: obtain after 12-lead ECG collection but prior to obtaining blood samples and prior to dosing (refer to [Section 7.1.5](#)).
- *Fasting blood samples*: after assessment of 12-lead ECG and vital signs but prior to dosing (refer to [Section 7.1.1](#)).
- *Serial blood samples for plasma PK, insulin, CCI* [REDACTED] as close as practically possible to the scheduled time (refer to [Schedule of Activities](#)).
- If the post-dose blood collection nominal time coincides with the nominal time of a meal, these blood samples should be collected just ***prior to*** meal/snack.
- *Other pre-dose procedures*: should be obtained/performed as close as possible to the scheduled time, but may be obtained before or after blood specimen collection.
- *Dosing*: must occur at the scheduled nominal time (refer to [Section 5.5](#)) and following pre-dose blood sample collection.

- ***If*** an intravenous catheter is placed for serial blood sample collections, ECGs and vital signs (pulse rate, BP) assessments should be either collected prior to the insertion of the catheter or sufficient rest period after catheter insertion introduced to minimize impact of catheter placement on these assessments.

6.2. Screening

Refer to the [Schedule of Activities Table 1](#) for the study procedures to be completed at the Screening visits. **The 3 screening visits are to be performed sequentially.**

- At Screen 1, subjects will be consented and all screening procedures (except assessment of liver fat by MRI-PDFF) undertaken to determine eligibility – refer to [Sections 4.1](#) and [4.2](#);
- **Only** after subjects are identified to be otherwise eligible, should they proceed with Screen 2 for another FibroScan® assessment as performed at Screen 1;
- **Following** confirmation of all eligibility at Screen 2, subjects should proceed to the Imaging center for the Screen 3 visit to undergo liver fat assessment via MRI-PDFF acquisition to assess whether they meet inclusion criterion #4, [Section 4.1](#).

Subjects will be screened **within 42 days** prior to the first dose of the blinded IP to confirm that they meet the subject selection criteria for the study. The investigator (or an appropriate delegate at the investigator site) will obtain informed consent from each subject in accordance with the procedures described in [Section 12.3](#).

In ***rare*** cases, subjects may be re-screened; however, this is permitted ***only*** when, due to ***logistical constraints***, the maximum period between the Screen 1 and Day 1 of **42 days** is exceeded. In such cases, all screening procedures must be repeated and the subject assigned a new 8-digit SSID number. Subjects must be deemed to meet all the eligibility criteria including assessment of liver fat via MRI-PDFF at Screen 3, under the new 8-digit SSID.

To prepare for study participation, subjects will be instructed on the use of Lifestyle Requirements ([Section 4.4](#)) and Concomitant Treatments ([Section 5.8](#)).

6.3. Study Period

Refer to the [Schedule of Activities](#) for the study procedures to be completed.

CCI

If a subject has any clinically significant, study-related abnormalities at the conclusion of a scheduled inpatient portion of the study, the Pfizer medical monitor (or designated representative) should be notified and the subject may be asked to remain in the CRU until such abnormalities are deemed not clinically significant, or it is safe for outpatient follow-up.

If the subject is unable or unwilling to remain in the CRU and/or when outpatient follow-up is deemed appropriate, the Pfizer medical monitor (or designated representative) should be so notified, and the investigator should make every effort to arrange follow-up evaluations at appropriate intervals to document the course of the abnormalities.

6.4. Follow-up

In this study, there are 2 follow-ups, as listed below:

- **1st follow-up is an on-site visit** where the subjects will return to the CRU between 7 to 10 days following the last dose of IP.
- **2nd follow-up is a telephone contact** that will occur 28 to 35 days following the last dose of IP. If the PI deems it necessary, this contact may be a visit.
- Refer to the [Schedule of Activities](#) for the study procedures to be completed at each of the 2 follow-ups.

6.5. Subject Withdrawal

Subjects may withdraw from the study at any time at their own request, or they may be withdrawn at any time at the discretion of the investigator or sponsor for safety (see also [Section 8.1.3](#)) or behavioral reasons, or the inability of the subject to comply with the protocol-required schedule of study visits or procedures at a given investigator site. The early termination visit applies only to subjects who are randomized and then are prematurely withdrawn from the study.

If a subject does not return for a scheduled visit, every effort should be made to contact the subject. The investigator or site staff should attempt to contact the subject twice. After 2 attempts, CRU staff may send a registered letter. If no response is received from the subject, the subject will be considered lost to follow-up. All attempts to contact the subject and information received during contact attempts must be documented in the subject's medical record. In any circumstance, every effort should be made to document subject outcome, if possible. The investigator should inquire about the reason for withdrawal, request that the subject return for a final visit, if applicable, and follow up with the subject regarding any unresolved AEs.

It may be appropriate for the subject to return to the clinic for final safety assessments to be scheduled as early as practically feasible following the decision to withdraw from the study. Subjects should be questioned regarding their reason for withdrawal. At the early-withdrawal visit, every effort must be made to complete the following assessments:

- Conduct an inquiry about any spontaneously reported AEs by asking the subject to respond to a non-leading question such as "how do you feel?"
- Full physical examination, if there is a new or open AE or clinically significant abnormal physical finding from the last visit (refer to [Section 7.1.3](#));

- Supine, single standard 12-lead ECG measurement (refer to [Section 7.1.6](#));
- Single, supine BP and pulse rate measurements (refer to [Section 7.1.5](#));
- Blood and urine specimens for clinical laboratory tests (refer to [Section 7.1.1](#));
- Blood sample for PK analysis for PF-06865571 (refer to [Section 7.2](#));

CCI

- Blood for cystatin C (refer to [Section 7.1.2](#));
- Blood for insulin (refer to [Section 7.3.4](#)).

Lack of completion of all or any of the withdrawal/early termination procedures will not be viewed as protocol deviations as long as the subject's safety was preserved.

If the subject withdraws from the study and also withdraws consent for disclosure of future information, no further evaluations should be performed and no additional data should be collected. The sponsor may retain and continue to use any data collected before such withdrawal of consent.

Withdrawal of consent:

Subjects who request to discontinue receipt of study treatment will remain in the study and must continue to be followed for protocol-specified follow-up procedures. The only exception to this is when a subject specifically withdraws consent for any further contact with him or her or persons previously authorized by the subject to provide this information. Subjects should notify the investigator in writing of the decision to withdraw consent from future follow-up, whenever possible. The withdrawal of consent should be explained in detail in the medical records by the investigator, as to whether the withdrawal is only from further receipt of investigational product or also from study procedures and/or posttreatment study follow-up, and entered on the appropriate CRF page. In the event that vital status (whether the subject is alive or dead) is being measured, publicly available information should be used to determine vital status only as appropriately directed in accordance with local law.

Lost to follow-up:

All reasonable efforts must be made to locate subjects to determine and report their ongoing status. This includes follow-up with persons authorized by the subject as noted above. All attempts should be documented in the subject's medical records. If it is determined that the subject has died, the site will use locally permissible methods to obtain the date and cause of death. If the investigator's use of a third-party representative to assist in the follow-up

portion of the study has been included in the subject's informed consent, then the investigator may use a sponsor-retained third-party representative to assist site staff with obtaining the subject's contact information or other public vital status data necessary to complete the follow-up portion of the study. The site staff and representative will consult publicly available sources, such as public health registries and databases, in order to obtain updated contact information. If, after all attempts, the subject remains lost to follow-up, then the last-known-alive date as determined by the investigator should be reported and documented in the subject's medical records.

7. ASSESSMENTS

Every effort should be made to ensure that protocol-required tests and procedures are completed as described. However, it is anticipated that from time to time there may be circumstances outside the control of the investigator that may make it unfeasible to perform the test. In these cases, the investigator must take all steps necessary to ensure the safety and well-being of the subject. When a protocol-required test cannot be performed, the investigator will document the reason for the missed test and any corrective and preventive actions that he or she has taken to ensure that required processes are adhered to as soon as possible. The study team must be informed of these incidents in a timely manner.

For samples being collected and shipped, detailed collection, processing, storage, and shipment instructions and contact information will be provided to the investigator site prior to initiation of the study.

Refer to [Section 6.1](#) for the recommended order of collection when multiple procedures are scheduled at the same timepoint.

7.1. Safety

7.1.1. Laboratory Tests

The following clinical laboratory tests will be performed at times defined in the [Schedule of Activities](#). Additional laboratory results may be reported on these samples as a result of the method of analysis or the type of analyzer used by the clinical laboratory; or as derived from calculated values. These additional tests would not require additional collection of blood. Unscheduled clinical laboratory measurements may be obtained at any time during the study to assess any perceived safety concerns.

Table 6. Clinical Laboratory Tests

Hematology	Chemistry	Urinalysis	Other
Hemoglobin Hematocrit RBC count MCV MCH MCHC Platelet count WBC count Total neutrophils (Abs) Eosinophils (Abs) Monocytes (Abs) Basophils (Abs) Lymphocytes (Abs)	BUN/urea Creatinine Plasma glucose (fasting) Calcium Sodium Potassium Chloride Total CO ₂ (bicarbonate) AST, ALT Total bilirubin Alkaline phosphatase GGT Total bile acids Uric acid Albumin Total protein Direct bilirubin ^d Indirect bilirubin ^d Serum cystatin C	pH Glucose (qual) Protein (qual) Blood (qual) Ketones Nitrites Leukocyte esterase Urobilinogen Urine bilirubin Microscopy ^a	
 • FSH^b • Urine drug test^c • Serology: HIV, HepBsAg, HepBcAb, HCVAb (and if positive, reflex HCV RNA)^c • A1AT^c • HbA1c^c • Ceruloplasmin^c • PT/INR^c
Additional Tests (Needed for Hy's Law)			

 • AST, ALT (repeat) • Total bilirubin (repeat) • Albumin (repeat) • Alkaline phosphatase (repeat) • Direct bilirubin • Indirect bilirubin • Creatine kinase • GGT • PT/INR • Total bile acids • Acetaminophen drug and/or protein adduct levels 			

a. Only if urine dipstick is positive for blood, protein, nitrites or leukocyte esterase.

b. At Screening only, in all females.

c. At Screening only.

d. Direct and indirect bilirubin measured only when total bilirubin is >ULN.

For a list of abbreviations, refer to [Appendix 1](#).

- The minimum requirement for drug screening includes cocaine, tetrahydrocannabinol (THC), opiates/opioids, benzodiazepines, and amphetamines.
- Subjects may undergo random urine drug testing at the discretion of the investigator. Drug testing conducted prior to dosing must be negative for subjects to receive IP.
- Estimated glomerular filtration rate (eGFR) will be calculated using the modification of diet in renal disease (MDRD) equation.

Any remaining serum/plasma from samples collected for clinical safety laboratory measurements at baseline and at all times after dose administration may be retained and stored for the duration of the study. CCI

CCI

These data will not be included in the clinical study report (CSR). Samples to be used for this purpose will be shipped to either a Pfizer-approved BBS facility or other designated laboratory and retained for up to 1 year following the completion of the study.

7.1.2. Serum for Cystatin C

Blood samples (approximately 2.5 mL) to provide a sufficient quantity of serum for analysis of cystatin C will be collected into appropriately labeled tubes at pre-specified nominal time points outlined in the [Schedule of Activities](#). GFR will be estimated from the cystatin C using the CKD-Epi-Cystatin C equation¹⁸ provided below.

- For serum cystatin C (Scys) ≤ 0.8 mg/L:

$$eGFR = 133 \times (\text{Scys}/0.8)^{-0.499} \times 0.996^{\text{Age}} [\times 0.932 \text{ if female}]$$

- For serum cystatin C (Scys) > 0.8 mg/L:

$$eGFR = 133 \times (\text{Scys}/0.8)^{-1.328} \times 0.996^{\text{Age}} [\times 0.932 \text{ if female}]$$

7.1.3. Physical Examinations

Physical examinations may be conducted by a physician, trained physician's assistant, or nurse practitioner as acceptable according to local regulation. A full physical examination will include head, ears, eyes, nose, mouth, skin, heart and lung examinations, lymph nodes, and gastrointestinal, musculoskeletal, and neurological systems. The limited or abbreviated physical examination will be focused on general appearance, the respiratory and cardiovascular systems, and subject-reported symptoms.

7.1.4. Body Weight

In this study, assessment of body weight will occur at the nominal time points specified in the [Schedule of Activities](#) per the following specifications –

- Weight will be recorded using a calibrated scale placed on a stable, flat surface;
- *During the inpatient stay*, the same scale will be used with the scale reporting weight in kilograms, and accuracy to the nearest 0.1 kg [ie, the device must be able to distinguish a difference between 68.4 kg and 68.3 kg];
- Measurement must be undertaken –
- At approximately the same time of the day, in the morning in the fasting state, at each nominal time point *while inpatient*;
- After the subject has been asked to void (ie, forced void);

- Under standard conditions (eg, subjects must wear light clothing with content of their pockets emptied or hospital gown **and not** be wearing shoes or bulky layers of clothing/jackets);
- With subjects remaining still while on the weighing scale.

7.1.4.1. Adjustment of Caloric Intake to Maintain Stable Body Weight

- Daily caloric intake, *while inpatient*, should be adjusted based on *each* serial assessment of body weight *after* Day 1 – refer to [Section 4.4.1](#);
- The initial caloric intake/menu assigned to each subject will be based on the Harris Benedict formula (sedentary lifestyle; to be provided to the site prior to study start) using the subject's body weight measured at screening;
- Caloric intake should be adjusted, on the days when body weight is assessed, to ensure that the subjects do not gain or lose body weight – defined as no more than ± 1.0 kg change in body weight on any day post Day 1 **compared to the body weight at Screen 1**;
- **NOTE:** on **selected** days when meals and snacks offered are to be identical (ie, Days -2, -1, 1, 14, and 15), while body weight measurements may occur on some of these days, adjustment to caloric content on these **selected** days must **not** occur.

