- g. At Screen 3 visit **after** confirmation of **all** other eligibility.
- h. Meals to be provided at approximately 0H, 4H, and 10H post AM dose and snack to be provided at approximately 12H post AM dose, as specified in Section 4.4.1. Day 16 meal(s) are optional, according to clinical research unit (CRU) practice.
- i. Dosing to occur with breakfast and snack, as specified in Section 4.4.1.

CCI

- k. PK samples to be collected prior to dose.

Table 2. Schedule of Activities – Study Days -1, 1, 7 & 14

[Procedures at 0H to be completed prior to dosing or similar clock time, in the case of Day -1]

Hours Relative to Dosing at 0H ^a	0	0.5	1	2	3	4	6	8	10	12	14	16	18	24
Continued inpatient stay at CRU	→	→	→	→	→	→	→	→	→	→	→	→	→	→
Adverse event monitoring	→	→	→	→	→	→	→	→	→	→	→	→	→	→
Body weight	x													
Triplicate, supine 12-lead ECG	x													
Single, supine vital sign assessment	x													
Blinded IP administration (Days 1, 7 and 14 only)	x ^b									x ^c				
Randomization (Day 1 only)	x													
Blood sampling for:														
- Clinical laboratory tests and serum cystatin C ^d (Days 1, 7, and 14 only)	x													
CCI														
- PF-06865571 PK (Day 14 only)	x		x	x	x	x	x	x		x				
- Serum triglycerides (Days -1, 1 and 14 only) ^d	x ^f			x		x	x	x	x	x	x	x	x	
CCI														
- Plasma insulin ^{d,g}	x													
Urine sampling for:														
- Urinalysis and microscopy, as appropriate (Days 1, 7, and 14 only)	x													
Meals ^h														
- Standardized meal	x					x			x					
- Snack										x				

- a. On Day -1, nominal time to approximately match clock time of collection planned on Day 1 to permit time-matched comparison.
- b. Dosing expected to occur with breakfast.
- c. Dosing expected to occur with snack as specified in [Section 4.4.1](#).

CCI

- g. Insulin samples collected in triplicate on Day -1 and Day 14. On Day 1 and Day 7, only 1 sample will be collected.
- h. Meals/snacks to occur on all days while inpatient; identical meals/snacks on Days -2, -1, 1, 14, and 15.

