Total duration of dosing PF-06865571/placebo in this study is proposed as 2 weeks, as supported by completed nonclinical toxicity studies in rats and monkeys. This duration is also expected to permit sufficient assessment of the primary pharmacology of PF-06865571 and its effect on liver fat. Given the current study is the first to administer repeated doses of PF-06865571 to subjects with NAFLD, a baseline day (Day -1) will permit assessment of safety (including triplicate ECGs) and tolerability, ie, change from baseline (CFB, within subject) and placebo-adjusted comparison of dose-response (between subject), as appropriate.

This study is also designed to assess the effect of PF-06865571 on other PD markers that are intended to provide insight into associated metabolic pathways. (CCI [REDACTED])

(CCI [REDACTED])

The serial collection of blood samples to permit assessment of PD effect in this study will assist in understanding the optimal dosing regimen to potentially characterize the dose (or exposure) response, as well as to build PK/PD understanding.

PF-06865571 is not anticipated to have a significant effect on body weight, however, to contain the influence of inpatient stay on liver fat, subjects will have their body weight assessed on serial days and their daily caloric intake adjusted to minimize change (both increase and decrease) in body weight while inpatient – refer to [Section 7.1.4](#).

CCI

Creatinine is actively secreted by OCT2/MATE in kidney. In the setting of OCT2/MATE inhibition, serum creatinine levels have been reported to increase slightly.¹⁷ In accordance with reported literature on OCT2/MATE inhibition, minor increases in serum creatinine have been observed in C2541002 with very limited/no change in cystatin. In order to better assess renal function in the setting of possible PF-06865571-induced OCT2/MATE inhibition resulting in spurious serum creatinine increases, serum cystatin C will be assessed as part of the standard safety labs, in addition to serum creatinine, in order to accurately interpret potential changes in glomerular filtration rate (GFR).¹⁸

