3. STUDY DESIGN

3.1. Study Overview

This will be a randomized, double-blind (sponsor-open), stratified, placebo-controlled, 3-arm (placebo, plus 2 active doses of PF-06865571), parallel-group study (refer to Figure 1).

Figure 1. Design of Study C2541005

A total of approximately 45 subjects (15 per arm) will be randomized at approximately 4 to 6 sites to ensure a minimum of 42 subjects complete the study (assuming an approximate 5% premature withdrawal rate). Subjects may be replaced at the discretion of the principal investigator (PI) and Sponsor. Subjects will be randomized to receive PF-06865571 (2 dosing regimens) or matching placebo (1 dosing regimen) in a 1:1:1 ratio.

For a given subject, the total study duration from Screen 1 to the follow-up phone call will be up to approximately 13 weeks. Screen 1 will occur within 42 days prior to the first dose of blinded IP (PF-06865571 or matching placebo). Eligible subjects who meet the entry criteria will progress to admission on the morning of Day -2, prior to lunch, for an 18-day (17-night) inpatient stay. While inpatient, subjects will receive blinded IP for 14 consecutive days and remain inpatient for approximately an additional 48 hours post AM dose on Day 14. Following discharge on Day 16, subjects will return for an on-site follow-up visit 7 to 10 days following the last dose of blinded IP, and a follow-up phone call (or visit, if necessary per the PI) 28 to 35 days following the last dose of blinded IP.

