- Any malignancy not considered cured (except basal cell carcinoma and squamous cell carcinoma of the skin); a subject is considered cured if there has been no evidence of cancer recurrence in the previous 5 years;

- Active placement of medical devices in/on thoracic or abdominal cavities such as pacemakers, defibrillators.
10. Subjects with any anatomical or pathological abnormality that would either preclude or tend to confound the analysis of study data, including any clinically significant abnormal findings on MRI obtained at Screen 3, by the Sponsor-identified central imaging vendor, or subjects meeting criteria for contraindication for MRI, including the following:
 - History of severe claustrophobia impacting ability to perform MRI during the study despite mild sedation/treatment with an anxiolytic;
 - Subjects with metal implants, devices, paramagnetic objects contained within the body, and excessive **or** metal-containing tattoos;
 - Subjects unable to lie still within the environment of the MRI scanner **or** maintain a breath hold for the required period to acquire images despite mild sedation/treatment with an anxiolytic;
 - Subjects with abdominal girth greater than the bore size of the site's MRI system.
 11. Subjects taking any prohibited concomitant medication(s) **or** those unwilling/unable to switch to permitted concomitant medication(s) [refer to [Section 5.8](#)];
 12. Weight loss of $\geq 5\%$ within 1 month prior to Screen 1;
 13. Pregnant female subjects; breastfeeding female subjects; female subjects of childbearing potential; fertile male subjects who are unwilling or unable to use highly effective method(s) of contraception as outlined in this protocol ([Section 4.4.4](#)) for the duration of the study and for **at least 28 days** after the last dose of IP;
 14. Blood donation (excluding plasma donations) of approximately 1 pint (500 mL) or more within 56 days prior to Screen 1 or during the study until the on-site follow-up visit;
 15. History of sensitivity to heparin or heparin-induced thrombocytopenia **only if** heparin is used to flush intravenous catheters;
 16. Treatment with an investigational drug within 30 days (or as determined by the local requirement) or 5 half-lives preceding the first dose of IP (whichever is longer);
 17. Subjects with known prior participation in a trial involving PF-06865571 (ie, received at least 1 dose of IP);

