3. ENDPOINTS AND BASELINE VARIABLES: DEFINITIONS AND CONVENTIONS

3.1. Primary Endpoint(s)

Relative change from baseline in whole liver fat at Day 15, as assessed by MRI-PDF. The relative change will be expressed in % unit, $[100 * (\text{relative change} - 1)]$. Baseline is defined as the planned measurement collected closest *prior to* dosing on Day 1.

The liver fat or the whole liver PDFF is calculated from the pre-defined individual segmental PDFFs labeled Segment I, II, III, IVa, IVb, V, VI, VII and VIII as follows:

Whole Liver PDFF = $\frac{\text{PDFFs for (Segment I + Segment II + Segment III + Segment IVa + Segment IVb + Segment V + Segment VI + Segment VII + Segment VIII)}}{\text{(number of segments assessed)}}$.

A minimum of 5 non-missing common segments is needed in order to calculate whole liver PDFF. All segments are equally weighted.

While deriving the relative change from baseline, the same segments are to be used at both baseline and post-baseline time points in the calculation of whole liver PDFF. For example, if at baseline PDFFs from all segments are available but, on Day 15, only 7 segments have non-missing results, whole liver PDFF will be calculated using the matching individual segmental PDFFs at *both* baseline and Day 15.

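### The inpatient weight-stability rule is anchored to Screen 1 weight, so it can steer subjects towards weight change between the two scans that form the primary endpoint

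*Protocol*

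**What the plan says.** Protocol 1.3.1 gives the purpose of weight control. To limit the influence of the inpatient stay on liver fat, daily calories are to be "adjusted to minimize change (both increase and decrease) in body weight while inpatient".

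Protocol 7.1.4.1 puts this into operation. Calories are adjusted at each weighing after Day 1, and stability means no more than 1.0 kg of change in either direction on any day after Day 1, "compared to the body weight at Screen 1". The starting menu also uses screening weight, through the Harris Benedict formula. A note protects the identical-meal days (Days -2, -1, 1, 14 and 15): "while body weight measurements may occur on some of these days, adjustment to caloric content on these" days is not allowed.

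Other provisions that bear on the reference weight:

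- Protocol 3.1: "Screen 1 will occur within 42 days prior to the first dose".
- Protocol 7.1.4: while inpatient, "the same scale will be used with the scale reporting weight in kilograms". The same-scale requirement does not reach back to Screen 1.
- Protocol 4.2, exclusion 12: weight loss of 5% or more is excluded only if it occurs "within 1 month prior to Screen 1".
- SAP 3.1, for the primary endpoint: "Baseline is defined as the planned measurement collected closest" before dosing on Day 1. Protocol 7.5.2 plans that scan for Day -2. The endpoint scan is on Day 15.

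**The concern.** The quantity that needs holding steady is weight between the Day -2 and Day 15 scans. The rule instead controls distance from a weight taken up to six weeks before first dose, possibly on another scale. Neither document gives another reference weight or limits drift between Screen 1 and admission.

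The rule can therefore fail in two ways. It can ask the site to change the weight of a subject who is already stable, and it can pass a subject whose weight has moved during the stay. Since weight is being controlled precisely because it may affect liver fat, either failure could add unexplained variation to the relative change in PDFF. The trial expects about 14 completers per arm and states power of at least 79%, so there is little room for avoidable noise.

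**Working it through.** **1. The plan's own power figure.** Inputs from Protocol 9.1: 25% reduction relative to placebo, SD 0.36 on the log-relative change, 1-sided alpha 0.10, 42 completers (14 per arm).

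- Effect: -ln(0.75) = 0.2877.
- SE of an arm difference: 0.36 × sqrt(2/14) = 0.1361.
- Power (normal) = Φ(0.2877/0.1361 − 1.2816) = Φ(0.833) = 79.7%.
- Power (t, 37 df: three arms, two covariates) = 79.1%.

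The stated figure of at least 79% reproduces.

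**2. What the rule requires.** Let d be the absolute gap in kg between admission weight and Screen 1 weight. Meeting the target at every weighing after Day 1 means being within 1.0 kg of Screen 1 weight.

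| d (kg) | Smallest change that meets the target | Largest change still counted as stable |
|---|---|---|
| 0.5 | 0 | 1.5 |
| 1.0 | 0 | 2.0 |
| 1.5 | 0.5 | 2.5 |
| 2.0 | 1.0 | 3.0 |
| 3.0 | 2.0 | 4.0 |

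The middle column is max(0, d − 1.0) and the last is d + 1.0. Changes are measured from admission weight. With Day -2 weight as reference, the middle column would be 0 for everyone and the last column 1.0. This step needs no outside assumption.

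**3. How many subjects, and how much change.** The documents do not give the Screen 1-to-admission difference. Assume it is normal with mean 0 and SD s. The proportion admitted outside the band is 2Φ(−1/s). If every such subject is brought exactly to the band edge, the mean-square change is 2[(s² + 1)Φ(−1/s) − sφ(1/s)].

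| s (kg) | Admitted outside band | RMS change (kg) |
|---|---|---|
| 0.5 | 5% | 0.054 |
| 1.0 | 32% | 0.388 |
| 1.5 | 50% | 0.826 |
| 2.0 | 62% | 1.295 |

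**4. Effect on the endpoint.** The documents do not give the liver-fat response to weight either. Assume b = 0.02 to 0.06 on the log scale per kg (2% to 6% relative PDFF). Added variance is (RMS × b)², compared with 0.36² = 0.1296.

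| Case | Added variance, as % of 0.1296 | Power, 14 per arm (normal) |
|---|---|---|
| Plan as stated | 0 | 79.7% |
| s = 0.5, b = 0.02, full correction | under 0.01% | 79.7% |
| s = 1, b = 0.04, full correction | 0.19% | 79.7% |
| s = 2, b = 0.06, half correction | 1.2% | 79.4% |
| s = 2, b = 0.06, full correction | 4.7% | 78.4% |

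For the last row, (1.295 × 0.06)² = 0.00604, so the SD rises from 0.36 to sqrt(0.1296 + 0.00604) = 0.368. The loss is 1.4 points; by the t calculation power goes from 79.1% to 77.7%. At 15 per arm, the added component of the SE of an arm difference is 1.295 × 0.06 × sqrt(2/15) = 0.028, against an existing 0.36 × sqrt(2/15) = 0.131. The two combine as squares, so the total SE rises by much less than 0.028.

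**The case against.** The strongest reply is that this hardly matters. The 1.4-point loss needs three extremes together: a drift SD of 2 kg, 6% per kg, and full correction to the band edge. A middle case leaves power unchanged to the first decimal, and neither input that sets the size is documented. That stands, and it limits the point to a wording correction.

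The rule is also weaker than a requirement. Calories should be adjusted; no withdrawal or exclusion is attached to missing the band. There is no per-protocol set (SAP 4.2), and the Full Analysis Set does not depend on weight. Adjustment is possible only on weighing days after Day 1 other than Days 14 and 15, and intake is capped at about 3,200 kcal (Protocol 4.4.1). This also stands: full correction of a gap of several kilograms is an upper bound. It does not make the target right, because any adjustment that is made is aimed at the wrong weight.

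Screen 1 weight is not careless either. It is taken at a fasted visit, the calibrated-scale, voiding and clothing conditions apply to it, and 42 days is a maximum. One might defend it as habitual weight, but neither document does so, and Protocol 1.3.1 states a different aim.

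Finally, SAP 6.6.5 summarises body-weight change by arm with differences from placebo, so an imbalance between arms would be visible. That helps interpretation but does not remove within-arm noise.

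**Conclusion.** The concern holds. The Screen 1 reference conflicts with the protocol's own aim: it can call for weight change during the stay in a subject who is stable, and it can count 2.0 kg of inpatient change as stable even in a subject admitted within the band. That conclusion follows from the text alone.

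The size is small and rests on two assumptions the documents do not supply. Over a drift SD of 0.5 to 2 kg and 2% to 6% relative PDFF per kg, added variance runs from under 0.01% to 4.7%, and the largest power loss is 1.4 points. The expected effect is noise rather than bias, since the rule is common to all arms and sites and image readers are blinded. The primary conclusion is not threatened. The reason to change the text is that it contradicts its purpose and is easily corrected.

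**What to change.** In Protocol 7.1.4.1, replace "compared to the body weight at Screen 1" with a comparison to the fasted inpatient body weight on Day -2, the day of the baseline scan. The Day -1 weight or the Day 1 pre-dose weight would also serve. Keep screening weight only for the initial Harris Benedict menu.

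The cost is one phrase. Body weight is already scheduled on Day -2 (Table 1) and on Days -1 and 1 (Table 2, "Study Days -1, 1, 7 & 14"), under the inpatient same-scale rule. No procedure, visit, sample size or analysis changes. A protocol amendment needs IRB/EC approval (Protocol 12.1), so once the study is under way the change is best bundled with another amendment.
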